#### Urine collection and assessment of gastrointestinal permeability

Differential sugar absorption tests will be used to provide a functional assessment of gastrointestinal permeability. For this test participants will consume 2 g sucralose dissolved in 180 mL water on the morning of study days 11, 39, and upon return to initial body mass (EOS). Sucralose is a sugar substitute commonly used as a sweetener in a variety of food products. Consumption of the solution will be conducted under staff supervision. Participants will then collect a urine sample 24-h after sugar substitute ingestion. Aliquots will be taken and frozen immediately. The sucralose concentration will be analyzed by PBRC. The sucralose ratio in the 24hr urine collection will provide measures of whole gut permeability. Prior to testing days, participants will undergo a 2-day washout period of sucralose- containing beverages and foods.

#### Determination of eating attitudes and behaviors

Several questionnaires will be administered with participants in a fasted state at SV2 and on study days 14, 42 and EOS to determine the effects of testosterone maintenance during energy deficit on eating behaviors and food cravings. We will also explore associations between these outcomes and gut microbiota composition. The Three Factor Eating Questionnaire (TFEQ) will be used to measure hunger, dietary restraint and disinhibition. Food cravings will be assessed using the Food Cravings Questionnaire-trait (FCQ-trait) and the Food Cravings Inventory 2 (FCI-2) which measures the frequency of cravings for specific types of foods. The TFEQ and FCQ-trait are publicly available. The FCI will be purchased from PBRC or used with permission. The TFEQ takes about 10 minutes, the FCQ-trait 5 minutes, and the FCI-2 5 minutes to complete and will be administered via the REDCap system.

#### **Objective III A-B: Statistics**

Data will be examined quantitatively and graphically for outliers and other artifacts that might have an undue impact on the analyses. Logarithmic or similar transformations will be applied when necessary to insure the validity of statistical procedures. All tests will be two-sided and considered statistically significant at  $P < 0.05$ . Data analysis will be completed using SPSS statistical software unless otherwise noted.

#### Physiological outcomes

Mixed-model repeated measures ANOVA will be used to test the effects of testosterone maintenance on changes in appetite, postprandial endocrine responses, intestinal permeability, and SCFA concentrations over time. Postprandial appetite ratings and responses of endocrine mediators of appetite will be summarized using area under the

curve and peak/nadir concentration prior to analysis. Mixed-models will include subject as a random factor, study day and group as fixed factors, and the day-by-group interaction. Akaike's information criterion will be used to determine appropriate covariance structures. When a statistically significant time-by-group interaction is detected ( $P < 0.05$ ), all possible within- and between-group comparisons will be completed, and the familywise error rate adjusted using the Bonferroni correction.

#### Psychological outcomes

Questionnaires will be scored according to questionnaire-specific procedures. Scores will then be analyzed by mixed-model repeated measures ANOVA. Mixed-models will include subject as a random factor, test session or study day and group as fixed factors, and the session-by-group or day-by-group interaction. Akaike's information criterion will be used to determine appropriate covariance structures. When a statistically significant time-by-group interaction is detected ( $P < 0.05$ ), all possible within- and between-group comparisons will be completed, and the familywise error rate adjusted using the Bonferroni correction.

#### Gut microbiota composition and metabolomics

Metabolomics data will be visualized using hierarchical average-linkage clustering and principal components analysis. Taxonomic data will be visualized using hierarchical average-linkage clustering and principal coordinates analysis of beta (i.e., between samples) diversity scores (e.g., Bray-Curtis, and weighted and unweighted UniFrac). Alpha (i.e., within-sample) diversity will be calculated for taxonomic data using Shannon, Simpson and Chao1 indices. Mixed-model repeated measures ANOVA will be used to test the effects of testosterone maintenance on changes in metabolite concentrations, alpha diversity, and the relative abundance of individual taxa over time. Models will include study day and group as fixed factors, and their interaction. The Benjamini-Hochberg correction will be used to control the false discovery rate for main effects of time, group and the time-by-group interactions resulting from taxa-specific models. When a statistically significant time-by-group interaction is detected ( $Q < 0.05$ ), post hoc within- and between-group comparisons will be completed and the familywise error rate adjusted using the Bonferroni correction. Linear discriminant analysis will be used to identify between-group differences in metabolite concentrations and relative abundances of taxa at each time point. Data analysis will be completed using SPSS, XLSTAT, R, Qiime or similar software as needed.

#### Relationships between gut microbiota composition, metabolites, and physiological and psychological outcomes

Changes in gut microbiota composition, metabolites, and physiological and psychological outcomes during DEF and ad libitum feeding will be examined separately by Pearson's correlation or Spearman's rank correlation as appropriate. False discovery rate will be controlled using the Benjamini-Hochberg correction. Procrustes analysis will be used to examine the relationship between gut microbiota composition and metabolite profiles. Redundancy analysis will be used to examine the amount of variance in physiological and psychological outcomes explained by gut microbiota composition and metabolite profiles. Data analysis will be completed using XLSTAT, R or similar software as needed.

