### **Objective I: Effects of exogenous testosterone during energy deficit and recovery.**

- A. Determine the extent to which maintenance of a eugonadal state by exogenous testosterone administration attenuates the effects of severe, sustained energy deficit on body composition (body mass, lean body mass and fat mass), skeletal muscle (mass, strength/power/endurance, proteomics, intramuscular regulators of metabolism, protein synthesis and proteolysis), metabolism (energy expenditure, substrate oxidation and nitrogen balance) and physiological status (androgens, stress and metabolic hormones, inflammation, hepcidin, iron status, circulating and intramuscular substrates and blood lipids).
- B. Determine the effects of exogenous testosterone administration during severe, sustained energy deficit on subsequent recovery of body composition, skeletal muscle, and metabolic and physiological status.
- C. Identify metabolomic and genetic biomarkers associated with habitual dietary intake and severe, sustained energy deficit and their predictive association with body composition, skeletal muscle, metabolism, and physiological status.
- D. Determine the extent to which exogenous testosterone administration modulates both metabolomic biomarkers and associations between the metabolome and diet, body composition, skeletal muscle, metabolism, and physiological status during severe, sustained energy deficit.

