- A. Determine the effects of severe, sustained energy deficit and associated hypogonadism on mental fatigue and other aspects of mood, cognitive performance, brain function and sleep.
- B. Identify metabolic biomarkers of fatigue and their association with cognitive performance and sleep during metabolic stress using global metabolomics.
- C. Determine the extent to which the detrimental effects of sustained energy deficit on mood, cognitive performance, and sleep are attenuated by pharmacological testosterone treatment.
- D. Determine the extent to which exogenous testosterone administration modulates associations between the metabolome, fatigue, and cognitive performance during sustained energy deficit.
- E. Identify genetic markers of mood, personality, cognitive performance, and sleep that predict, in part, responses to energy deprivation and testosterone treatment.

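### Correlations of metabolites and microbiota with outcomes have no arm term, so a testosterone effect on both variables can distort them, and no planned analysis tests whether testosterone modifies the metabolome associations named in Objectives I-D and II-D

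*Combined protocol and SAP*

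**What the plan says.** Two sets of statements matter.

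**Objectives.** Objective I, item D, asks how far testosterone "modulates both metabolomic biomarkers and associations between the metabolome and diet, body composition, skeletal muscle, metabolism, and physiological status". Objective II, item D, asks how far it "modulates associations between the metabolome, fatigue, and cognitive performance during sustained energy deficit". For the microbiota, Objective III-B, item B, asks only that associations be identified.

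**Analyses.** The only association analysis described is the last subsection of the Objective III A-B statistics. Changes in microbiota, metabolites and "outcomes during DEF and ad libitum feeding will be examined separately by Pearson's correlation", or by a rank correlation where that suits. On multiplicity: "False discovery rate will be controlled using the Benjamini-Hochberg correction". A Procrustes analysis compares microbiota with metabolite profiles, and "Redundancy analysis will be used to examine the amount of variance in physiological and psychological outcomes explained by gut microbiota composition and metabolite profiles". None of these states an arm term, a split by arm or an interaction.

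The other statistics sections model levels, not associations. The Objective I models have day, group and their interaction. The Objective II analyses are factorial ANOVAs. The subsection on microbiota composition and metabolomics models each metabolite or taxon on day, group and their interaction.

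**The concern.** DEF is defined as the arm without testosterone in the Executive Summary, the Experimental Design and the Randomization section. In the correlation sentence it is paired with ad libitum feeding, which suggests a phase. Two analysts could run different analyses from that sentence.

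- **DEF as the deficit phase.** Both arms are pooled. Two variables that testosterone moves will correlate across the pooled sample even if they are unrelated within each arm. Opposite movements can hide a real association.
- **DEF as the arm.** There is no pooling in the deficit phase, but the DEF+TEST participants are left out. The recovery-phase correlation still has no arm term.

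On either reading, the association is not compared between arms, which is what the modulation objectives ask. At stake is whether a metabolite reported as a marker of muscle preservation carries information beyond the fact that testosterone was given.

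**Working it through.** **1. The plan's own figure.** Table 2 gives lean-mass losses of 3.0 and 2.25 kg with SD 0.75, so the standardised effect is (3.0 − 2.25)/0.75 = 1.0. Per group, n = 2 × (1.960 + 1.282)² / 1.0² = 21.0, rounded up to 22, as stated. The t-test version gives 22.02 (power 0.8997 at 22). No power or sample size is given for any association analysis.

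**2. Correlation induced by pooling.** Let testosterone shift the outcome by d1 and the marker by d2, in within-arm SD units, with 1:1 allocation and within-arm correlation ρ. Pooling adds d1·d2/4 to the covariance and d²/4 to each variance:

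r = (ρ + d1·d2/4) / √[(1 + d1²/4)(1 + d2²/4)]

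Inputs: d1 = 1.0 (Table 2); 25 completers per group (Power analysis); ρ = 0. The documents give no marker shift, so d2 is assumed and shown as a range. With n = 50 the critical |r| is 0.279. Rejection rates are from 40,000 simulated trials per row, Pearson, two-sided 0.05, one feature, no multiplicity correction.

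| d2 (SD) | Induced r | Pooled rejection | Arm-adjusted rejection |
|---|---|---|---|
| 0 | 0 | 5% | 5% |
| 0.5 | 0.125/√(1.25 × 1.0625) = 0.11 | 12% | 5% |
| 1.0 | 0.25/√(1.25 × 1.25) = 0.20 | 29% | 5% |
| 1.5 | 0.375/√(1.25 × 1.5625) = 0.27 | 49% | 5% |
| 2.0 | 0.5/√(1.25 × 2) = 0.32 | 65% | 5% |

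**3. Masking.** Take ρ = 0.3 with shifts of 1 SD in opposite directions. Pooled r = (0.3 − 0.25)/1.25 = 0.04, and the pooled test rejects in about 5% of trials. The arm-adjusted test rejects in about 56%.

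**4. Does the protocol expect both variables to move?** Yes. Hypothesis D under Objective I predicts a testosterone-driven metabolomic signature linked to preserved muscle mass. Hypothesis D under Objective II predicts the equivalent for fatigue and mental performance. Table 2 assumes the lean-mass effect.

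**5. Is modification tested anywhere?** The Objective I and II models contain no metabolite term. The group-by-day metabolite models cover whether testosterone changes metabolite levels, which is the first half of I-D. Nothing covers the association half of I-D, or II-D.

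**6. Power of a modification test.** Fisher's z for a difference in r between arms has SE = √(2/(25 − 3)) = 0.302.
- r of 0 vs 0.3: z difference 0.310, ratio 1.03, power 0.18; 80% power needs 167 per arm.
- r of 0 vs 0.5: z difference 0.549, ratio 1.82, power 0.45; 80% power needs 56 per arm.
- At 25 per arm, 80% power needs r of 0 vs 0.69.

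All are before Benjamini-Hochberg, which lowers power further.

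**The case against.** **The decision rule is Benjamini-Hochberg, not unadjusted 0.05.** This stands as a limit on the size. In a further simulation with an assumed 100 to 300 features, 5 to 20% of them shifted by testosterone, the share of shifted features declared after correction was 0.1–0.3% at 0.5 SD, 1–3% at 1.0 SD, 4–11% at 1.5 SD and 12–25% at 2.0 SD. The correction makes declarations much rarer. It does not change what a declared correlation means, because one induced by arm is a real marginal correlation and not a chance finding.

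**Testosterone need not create these correlations.** A reader might infer that it always does. The documents do not support that: a marker that testosterone does not move is unaffected (5% rejection in the first row), and under the arm reading of DEF the deficit-phase correlation is not pooled at all.

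**The correlation subsection serves Objective III.** A reader might infer that modification is also an unmet objective for the microbiota. It is not, because Objective III-B asks for associations only. The missing test belongs in the Objective I and II statistics.

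**A marginal correlation is a legitimate description.** It is, if labelled as such. An arm-adjusted estimate can stand beside it.

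**The absence of arm adjustment is inferred from silence.** True, but the neighbouring subsections name group explicitly, and a pre-specified plan should do so here too.

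**Conclusion.** The concern holds in a limited form. As written, the association analyses have no arm term and turn on an ambiguous label. If the arms are pooled, correlations can be created, inflated or masked wherever testosterone shifts both variables. For a single test at unadjusted 0.05, false rejection runs from about 5% with no marker shift to about 29% at 1.0 SD and 65% at 2.0 SD. That rests on the Table 2 effect, 25 per arm, zero within-arm correlation and assumed marker shifts. The recovery phase was not quantified.

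Separately, and whatever the effect size or the meaning of DEF, the association half of Objective I-D and Objective II-D have no between-arm test. A reader might conclude that I-D cannot be answered at all. That goes too far, since the effect of testosterone on metabolite levels is modelled.

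These are secondary analyses. The lean-mass comparison on which the trial was sized is not affected.

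**What to change.** In the Objective III A-B subsection on relationships:
- replace DEF by the deficit phase (both arms);
- report associations adjusted for arm (partial correlations, rank-based where needed), with the marginal correlation beside them if wanted and labelled as marginal;
- condition the redundancy analysis on arm, and say how arm is handled in the Procrustes analysis.

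In the Objective I and II statistics, for the metabolome associations named in I-D and II-D, add a linear model of change in outcome on change in metabolite, arm, arm-by-metabolite interaction and the age stratum used in randomization. Treat the interactions as their own Benjamini-Hochberg family and label them exploratory.

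The cost is SAP wording and up to three degrees of freedom beyond a simple correlation (arm, interaction, age stratum), with no new data or participants. Because interaction power is low, estimates with confidence intervals should be reported and a non-significant interaction should not be read as evidence of equal associations.

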## **Data and Specimen Management**

Study participants will be assigned unique subject identification (ID) numbers. Study subject ID numbers will be used on all data collection instruments, to include questionnaires, data collection forms, biological specimen tubes, and computer records. A master list linking the participants' names and ID numbers will be kept in a password-protected computer file with access restricted to the PI and study navigator. Biological samples that are moved off-site (including to USARIEM) for analysis will not contain any personally identifiable information and will be labeled with only the unique subject ID numbers. Staff at these sites will not have access to the master list at any time.

Data collection forms will be kept under lock and key, or password-protected if computerized, and under the control of the PI, associate PIs, and project coordinator. Only personnel assigned to the research study by the PI will have access to the data. Hard-copy data records will be stored for a minimum of 3 years and a maximum of 5 years from the time the study is completed and then destroyed.

The PBRC has a fully integrated, campuswide, automated data management system. All data are entered into a Central Database using existing methodology that has been fully validated and undergoes continuous quality assurance by the PBRC Research Computing Core and NORC. Most data are automatically uploaded from the instruments that measure the endpoint. All self-report inventories and questionnaires will be completed in REDCap via surveys. Participants will be asked to complete the survey via laptop, computer, or tablet. Data will be exported from REDCap for analysis. Exercise testing data will be downloaded from the Parvo Medics' TrueOne® 2400 cart directly following each test and reviewed for integrity. All data are backed up daily, and the Research Computing Core at the PBRC oversees all data management.

Blood, muscle, and urine samples will be stored frozen at PBRC until analysis can be completed. Specific muscle, saliva, and blood samples for proteomic and body water assessments will be frozen for future analysis. Specific muscle and blood samples will be shipped to MyoSyntax for further analysis. Fecal samples will be initially processed at PBRC and stored frozen until analysis. Fecal samples or bacterial DNA extracted from fecal samples will be frozen and shipped to NSRDEC and the Broad Institute (Cambridge, MA) for analysis. Packaging and shipping of biological samples will be overseen by the PI, associate PIs, or study navigator, and will be completed in accordance with International Air Transport Association regulations to ensure that viable biological samples reach their intended destination.

Any blood, muscle, urine, or fecal samples remaining after analysis will be stored indefinitely to assess biomarkers associated with the study outcomes. This includes bacterial RNA analysis in collected fecal samples, metabolomics analysis in archived fecal/plasma/serum samples, and any biomarkers of nutritional status not currently identified in the protocol. Any use of the samples outside of this defined protocol will be submitted as a protocol amendment or a new protocol.

## **Standardization of Procedures and Quality Control**

The research team has extensive experience using the procedures and methods required to conduct this study. Standard operating procedures in place throughout the units at Pennington Biomedical will be utilized for repeatable, valid data collection and

quality.

## **Data Analyses**

See specific statistic sections listed under each objective.

## **Provisions to Monitor the Data to Ensure the Safety of Subjects**

The PI and/or IRB of record will appoint a Research Monitor or monitors to ensure that voluntary participation is clearly and adequately stressed during the recruitment process. The monitor may be a member of the DSMB. The appointed DSMB member to serve as the Research Monitor is [name]. This appointee will also ensure that the information provided about the research is clear, adequate and accurate. He can be called upon to interview human subjects, consult with others outside of the study or with the investigators. He will have the responsibility to promptly report his observations and finding to the IRB or other designated official. The research monitor has the authority to stop the research protocol in progress, remove an individual subject from the protocol and take whatever steps are necessary to protect the safety and well-being of human subject until the IRB can assess the monitor's report.

## **Data and Safety Monitoring Board**

This study will use a data and safety monitoring board (DSMB). The DSMB will receive quarterly reports via email. One or more meetings each year may be conducted in person or via conference call if deemed appropriate by the DSMB chair. Prior to the start of recruitment the DSMB will give formal approval of the study protocol and informed consent.

- Size and Composition: The DSMB will consist of 4 members both internal and external to the Pennington Biomedical Research Center. The planned composition is as follows: Biostatistician (1), Exercise Physiologist (1), Clinician (1), Layperson (1)
- Major Responsibilities of Members:
  - Sign and abide by a statement of confidentiality
  - Disclose any actual or potential conflicts of interest
  - Oversee safety of participants to include review of adverse events
  - Review reports of related studies as appropriate
  - Review major proposed modifications
  - Monitor recruitment and adherence
- Reports: Following each meeting, the DSMB will provide written documentation regarding findings for the study as a whole and any relevant recommendations related to continuing, changing, or terminating the study. All DSMB recommendations will be submitted to the Principal Investigator and/or his designee, with a copy provided to the Pennington Biomedical Research Center IRB. Annually, the DSMB chair will provide a written summary report approving that the study can continue.
- Qualifications and Responsibilities of the Safety Officer: The Safety Officer for this trial will be familiar with the adverse event definitions and reporting requirements for the study. The Safety Officer will review reports sent by the study coordinator

as they occur and will determine whether there is any corrective action or stopping rule violation. The safety officer will send written documentation of the decision to the PI.

## Adverse Events

**Serious adverse events** are defined to include:

- Death
- A life-threatening event
- Severe illness including worsening of a pre-existing condition, injury or accidents
- An inpatient hospitalization, surgical procedure, or a treatment to prevent a SAE
- A permanent disability or incapacity
- A clinically significant abnormal laboratory or diagnostic test result
- Any other event that, in opinion of the principal investigator or study physician, might have resulted in a serious adverse event if medical intervention had not been initiated

For this trial's purposes, an **adverse event or experience** is defined as any health-related unfavorable or unintended medical occurrence that happens after randomization. Examples of Adverse Events include but are not limited to the following:

- A clinically significant laboratory or clinical test result at follow up assessments
- An event that results in 3 consecutive missed exercise sessions
- An event that requires a visit to a physician because it alters participant's ability to do physical activity
- An event that occurs as a result of a study procedure which is not listed in the Risks section of the consent

Adverse events will be reported to the study PI, study coordinator, Chair of IRB, Chair of the study DSMB, and Safety Officer throughout the trial as necessary. Adverse event data will be collected from Baseline (Day 0) until the final closeout visit. Adverse Events classified as serious will be reported from the date of consent through the final closeout visit. Adverse Event Data will be analyzed quarterly, but serious or life-threatening adverse events require immediate reporting and follow-up. We anticipate most adverse events will be mild and the participant will be able to resume intervention activities within a day or two of reporting the event.

In the event an adverse event occurs on campus results in a serious or life threatening situation, the investigator or other project staff present will begin emergency measures, as appropriate, and call 911.

- For minor physical injury, the individual will be encouraged to see a health care practitioner of his or her choice.
- If the study participant experiences psychological or emotional distress, the project staff will cease research activities and attempt to calm and reassure the participant. The participant will be directed to an appropriate health care practitioner for further assessment and treatment as needed.

- The investigator and/or project staff will record detailed narrative notes describing the adverse event they witnessed or that was reported by participant. The Medical Safety Officer will complete the form Notification of an Adverse Event.

Adverse Event reporting will follow the requirements of the IRB of the Pennington Biomedical Research Center. Serious adverse events that are unexpected and related to the study will be reported within 48 hours. Other adverse events that are not serious but are unexpected and are associated with the study procedures will be reported within 10 days.

